In the present study, we aim to compare the diagnostic yield of Robotic-nCLE-guided TBNA for lung cancer diagnosis to conventional Robotic-guided TBNA using the final diagnosis (histology or follow-up) as the standard reference. Furthermore, we will create an image atlas of the characteristics of nCLE-images in PPNs. Also, we aim to describe tumor types based on in-vivo characteristics. Improved characterization of distal lung lesions might lead to improved and quicker cancer diagnosis and patient care.

Background: nCLE imaging of PPNs under bronchoscopic guidance is feasible and safe.

Primary objective:

To compare the first-pass diagnostic yield of the sequential needle passes (ROSE) between the Robotic-nCLE-guided TBNA arm and the Robotic- guided TBNA arm in PPNs.

Primary endpoint:

Increase of the first-pass diagnostic yield by 20%, from 70% to 90%, between Robotic-nCLE-guided TBNA arm and the Robotic- guided TBNA arm in PPNs.

Secondary objectives:

1. To compare the per-patient diagnostic yield (cumulative pass diagnostic yield: cumulative number of passes until five cumulated passes) of Robotic-nCLE-guided TBNA arm to that of Robotic-guided TBNA arm in PPNs.
2. To compare the proportion of patients with lung cancer treatment in the Robotic-nCLE-guided TBNA arm to that of the Robotic-guided TBNA arm in PPNs.
3. To compare the proportion of patients with follow-up (video-assisted thoracoscopic surgery (VATS) or TTNA or TBNA procedures) in the Robotic-nCLE-guided TBNA arm to that of the Robotic-guided TBNA arm in PPNs.
4. To compare the number of passes needed to obtain a final diagnosis of Robotic-nCLE-guided TBNA to that of Robotic-guided TBNA in PPNs.
5. To assess the diagnostic performance (sensitivity, specificity, PPV, NPV, accuracy) of the sequential cumulative nCLE passes and the sequential cumulative ROSE passes using the final diagnosis as a reference.
6. Feasibility: obtain adequate CLE video footage in >80% of the PPN punctures.
7. To assess the safety of nCLE imaging, as defined by:
 - a. The number and frequency of all AE/SAE from the start of the procedure until end of 12-month follow-up;
 - b. The number and frequency of nCLE procedure-related AE/SAE from the start of the procedure until end of 12-month follow-up.
8. To assess the reproducibility of nCLE criteria with regard to the reference standard. Three nCLE characteristics for the detection of malignancy were identified during Wijmans et al. study [10]:

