The biopsy results can be classified into three categories: positive results, including malignant or benign lesions confirmed by a follow-up period, or negative results, including [18] intermediate histological samples, such as chronic inflammation, organizing pneumonia, or atypical cells without sufficient features to ascertain malignancy; or [22] indeterminate samples, such as normal lung tissue or insufficient sample size [6]. The tissue samples that produce intermediate and indeterminate samples should be further evaluated according to recommended guidelines for the management of pulmonary nodules.

In this study, the diagnostic yield of the bronchoscopic procedure (Robotic-guided TBNA or Robotic-nCLE-guided TBNA) will be defined as the proportion of patients in whom the bronchoscopic procedure yield a definitive diagnosis out of the total number of patients that have received the diagnostic procedure. This value is affected by the lesions' sizes, locations, and the existence of a bronchus sign or an airway leading directly into the lesion [23].

Primary objective:

To compare the first-pass diagnostic yield of the sequential needle passes (ROSE) between the Robotic-nCLE-guided TBNA arm and the Robotic-guided arm in PPNs.

Secondary objectives:

[figure not shown]
1. To compare the per-patient diagnostic yield (cumulative pass diagnostic yield: cumulative number of passes until five cumulated passes) of Robotic-nCLE-guided TBNA to that of Robotic-guided TBNA in PPNs.
2. To compare the proportion of patients with lung cancer treatment in the Robotic-nCLE-guided TBNA arm to that of the Robotic-guided TBNA arm in PPNs.
3. To compare the proportion of patients with follow-up (video-assisted thoracoscopic surgery (VATS) or TTNA or TBNA procedures in the Robotic-nCLE-guided TBNA arm to that of the Robotic-guided TBNA arm in PPNs.
4. To compare the number of passes needed to obtain a final diagnosis of Robotic-nCLE-guided TBNA to that of Robotic-guided TBNA in PPNs.
5. To assess the diagnostic performance (sensitivity, specificity, PPV, NPV, accuracy) of the sequential cumulative nCLE passes and the sequential cumulative ROSE passes using the final diagnosis as a reference.
6. To assess the feasibility by obtaining adequate CLE video footage in >80% of the PPN punctures.
7. To assess the safety of nCLE imaging, as defined by:

- a. The number and frequency of all AE/SAE from the start of the procedure until end of 12-month follow-up

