- b. The number and frequency of nCLE procedure-related AE/SAE from the start of the procedure until end of 12-month follow-up
- 8. To assess the reproducibility of nCLE criteria to the reference standard. Three nCLE characteristics for the detection of malignancy were identified during Wijmans et al. study [10]:
 - a. Dark enlarged pleomorphic cells;
 - b. Dark cell clusters consist of overlapping cell structures ('dark clumps') and
 - c. Continuous movement of the cells in one direction ('directional streaming').
- 9. To create an nCLE image atlas for malignant characteristics in PPNs.

3. Study Design

This is a randomized, controlled, interventional, comparative prospective multi-center study. In total, a maximum of 118 consecutive patients with a (suspected) PPN who are referred for a diagnostic bronchoscopic (Robotic-guided TBNA) procedure will be considered for enrollment. The estimated duration of the study is 24 months. Patients will be consecutively recruited and randomly assigned to undergo Robotic-guided TBNA (n=59) or Robotic-nCLE-guided TBNA (n=59).

Only patients in the nCLE arm will receive intravenously administered fluorescein before the start of the Robotic procedure. During the nCLE procedure, an 18G needle enters the targeted tissue, followed by an nCLE AQ-Flex™ 19N Confocal Miniprobe™ (Mauna Kea Technologies, France) through the biopsy needle, to obtain real-time imaging. nCLE imaging will be performed in the PPNs with a total estimated time for research measurements of 10 minutes. nCLE imaging will be performed for each sequential TBNA pass/sampling within the lung nodule lesion and each TBNA path cytopathological result will be correlated with the nCLE sequence acquired for that TBNA pass. TBNA sampling will end when sufficient diagnostic material will be found with ROSE (as assessed by the cytopathologist) or when the physician performing the procedure judges that the number of samplings/passes is adequate. ROSE will be performed by a cytopathologist.

4. Study Population

Population (base)

Patients with a PPN referred for diagnostic bronchoscopic/endosonographic workup tissue sampling based on standard (PET-) CT imaging

Inclusion criteria

To be eligible to participate in this study, a study subject must meet all of the following criteria:

- ≥ 21 years of age
- Suspected PPN
- Nodule size in CT between 8 mm and 30 mm (largest dimension)

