- Ability to understand and willingness to sign a written informed consent and HIPAA consent document

Exclusion criteria

- Inability or non-willingness to provide informed consent
- Failure to comply with the study protocol
- Patients with known allergy for fluorescein or risk factors for an allergic reaction
- Use of beta-blocker within 24 hours before the start of the bronchoscopic procedure
- Possibly pregnant, pregnant or breastfeeding women
- Patients with hemodynamic instability
- Patients with refractory hypoxemia
- Patients with a therapeutic anticoagulant that cannot be held for an appropriate interval before the procedure
- Patients who are unable to tolerate general anesthesia according to the anesthesiologist
- Patient undergoing chemotherapy

Intra-operative Exclusion/Stopping Criteria:

- The lesions are unable to be localized/confirmed by bronchoscopy
- The procedure will be terminated if the patient develops a significant procedural complication as determined by the treating physician
- The procedure will be terminated if the patient develops hemodynamic instability as determined by the treating physician

Sample size calculation

A bronchoscopic TBNA (Robotic-guided TBNA or Robotic-nCLE-guided TBNA) will be regarded as successful when histological confirmation of the diagnosis is achieved and matches the final diagnosis. If additional TBNA passes or tests, e.g., further bronchoscopies, surgery, etc., are needed to establish the diagnosis, the TBNA pass will be regarded as non-diagnostic.

We will calculate TBNA diagnostic yield for the cumulative number of passes until five cumulated passes for both the Robotic-guided TBNA and Robotic-nCLE-guided TBNA arms. It is anticipated that sequential passes at a target site will result in stepwise yield increments to a plateau. Every needle pass at a location will be reported separately and entered into a database to provide yields after each sequential pass.

Proportional data will be compared using a Chi-squared test of contingency tables or Fisher's exact test on 2x2 contingency tables in the case of very small counts (<5).

First- and cumulative-pass diagnostic yields:

Diagnostic yields for the different cumulative passes are defined as follows:

1. First-pass diagnostic yield is calculated as the proportion of patients for which first-pass TBNA during the bronchoscopic procedure yielded a definitive diagnosis out of the total number of patients that have received a diagnostic procedure.

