During the nCLE procedure the bronchoscopist will judge quality of the image, lung lesion detection, and presence of malignancy. The bronchoscopist will be trained in nCLE image evaluation.

Validation session

The trained raters will evaluate nCLE videos of all 59 patients as a randomized data-set and be blinded to the patient history and cytologic/pathologic diagnosis. Videos used for the training session will be excluded. The results of the nCLE video reviews will be compared to the corresponding cytological or histopathological results. The first session will be performed to assess the nCLE characteristics, image quality and confidence and will be used to calculate the inter-observer agreement (IOA) between the raters for detecting malignancies based on nCLE videos. The second session will be performed by the same group of raters, after a 2-week wash-out period, using the same set nCLE videos in a different order to assess the intra-observer reliability (IOR).

Pathological examination

During bronchoscopy, the sites suspected of malignancy will be evaluated with nCLE. In the case of positive tumor cytology (nodes/tumor) or histology (tumor), this will be the reference standard for the nCLE images. In the case of tumor negative cytology or histology, additional surgical/pathological staging or clinical/radiological follow-up will be available.

Cytological aspiration (standard procedure)

During the bronchoscopic procedure, the cytological aspirations will be evaluated on-site by a cytopathologist (ROSE). The appearance of cancer cells will be reported and shown on screen to the endoscopist. Definitive diagnosis of the sample follows after re-evaluation by a staff member of the pathological department. No additional samples will be taken for the research protocol, nor will the research protocol interfere with the pathological diagnostic protocol.

Histological evaluation

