- 3) the continuous movement of a part of the cells in one direction ('directional streaming')

These criteria will be evaluated qualitatively.

New nCLE characteristics in malignant and benign lung lesions could also be identified during this study. An imaging atlas of nCLE images will also be built for the different tumor types on in-vivo characteristics. The department of pathology will be strongly involved in this project.

nCLE-video images will be reviewed and diagnosed retrospectively, independently, and blindly by investigators, expert readers, and pathologists.

The diagnostic yield will be tested to give the likelihood that nCLE will provide the information needed to establish a diagnosis.

Correlation analysis will also be performed between:

- nCLE imaging results and digital images of cytological or histopathological results
- nCLE imaging results in different tumor types.

8. End Points

Primary endpoint: The definitive diagnosis will serve as the reference standard for the calculation of study endpoints. The study pathologists will not be aware of nCLE results. The primary endpoint of this study will be the first-pass diagnostic yield, as defined in the section "Sample size calculation", i.e. and is calculated as the proportion of patients for which first-pass TBNA during the bronchoscopic procedure yielded a definitive diagnosis out of the total number of patients that have received a diagnostic procedure

Secondary endpoint: The secondary outcome of this study will be the per-patient diagnostic yield, calculated as the proportion of patients in whom the bronchoscopic procedure yielded a definitive diagnosis out of the total number of patients that have received a diagnostic procedure.

Third endpoint: The third endpoint for patient management will be assessing the clinical impact of nCLE by determining the proportion of patients with a correct change in definitive diagnosis and the associated change in management plan with nCLE.

First-pass diagnostic yield:

The study is designed to enroll 118 patients who will be randomly assigned 1:1 to Robotic-guided TBNA alone or Robotic-nCLE-guided TBNA for a statistical power of 80% with a 2-sided significance level of 0.05 to detect an increase of the primary study endpoint (per pass TBNA diagnostic yield) of at least 20%, from 70% to 90%, between the Robotic-guided TBNA and the Robotic-nCLE-guided TBNA.

Per patient diagnostic yield (cumulative pass diagnostic yield) and performance:

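### Neither cytology reading behind the primary first-pass yield is masked to treatment arm, and the requirement to match the final diagnosis closes only part of that gap

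*Combined protocol and SAP*

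**What the plan says.** **Which reading.** The primary objective, in Section 1 and again in the objectives before Section 3, is "To compare the first-pass diagnostic yield of the sequential needle passes (ROSE) between the Robotic-nCLE-guided TBNA arm" and the control arm. Section 8 defines the endpoint as "calculated as the proportion of patients for which first-pass TBNA during the bronchoscopic procedure yielded a definitive diagnosis", over all patients who received a diagnostic procedure. Under Cytological aspiration, Section 5 says that "the cytological aspirations will be evaluated on-site by a cytopathologist (ROSE") and then that "Definitive diagnosis of the sample follows after re-evaluation by a staff member of the pathological department".

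**What counts as success.** Under Sample size calculation, Section 4 requires histological confirmation that agrees with the final diagnosis. A pass is scored non-diagnostic if further passes or tests are needed. The final diagnosis draws on up to 12 months of follow-up (Section 5, Final Diagnosis).

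**When sampling stops.** Section 3: "TBNA sampling will end when sufficient diagnostic material will be found with ROSE (as assessed by the cytopathologist"), or when the operator judges that enough passes have been made.

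**What the reader may know.** Section 8: "The study pathologists will not be aware of nCLE results". The other masking statements (Section 5, nCLE analysis and Validation session; Section 7, Reproducibility) concern the review of nCLE videos, which does not feed the primary endpoint.

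**How the arms differ.** Only the nCLE arm receives fluorescein and the probe, and the bronchoscopist judges malignancy on the image during the procedure. Imaging is estimated at 10 minutes in total. No sham is described.

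**The concern.** Whether a first pass is diagnostic is a graded judgement when the material is scant or atypical. In a comparison where the arms can be told apart, such a judgement is protected from expectation only if the reader does not know the arm. The ROSE cytopathologist reads on-site and shows cancer cells on screen to an operator who, in one arm, has just interpreted a confocal image. The later re-evaluation is further from the procedure, but nothing says that its reader is kept from knowing the arm.

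Being masked to nCLE results is not the same as being masked to arm. A reader who knows only that imaging took place may still expect better needle placement. The sentence in Section 8 also gives no means of keeping the results from an on-site reader.

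Two outcomes are exposed. A more lenient call in the nCLE arm raises its first-pass yield. A lenient ROSE call also ends sampling earlier, which affects pass counts and cumulative yields.

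**Working it through.** **1. The plan's own figure.** Inputs from Section 4: yields of 70% and 90%, 80% power, two-sided 0.05, 1:1 allocation. With unpooled variance,

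n = [0.70×0.30 + 0.90×0.10] × (1.960 + 0.842)² / 0.20² = 0.30 × 7.849 / 0.04 = 58.87, so 59 per arm.

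The stated 59 reproduces. Masking the reader does not change it.

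**2. Which readings are masked to arm.**

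| Step | Where | Masked to nCLE results | Masked to arm |
|---|---|---|---|
| On-site ROSE call | Sections 3 and 5 | Section 8, if ROSE readers count as study pathologists; no means given | Not stated |
| Pathology re-evaluation | Section 5 | Section 8 | Not stated |
| Operator's decision to take another pass | Section 3 | No; the operator reads the image | No |
| nCLE video raters | Sections 5 and 7 | Not applicable | Not relevant to the primary endpoint |

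Section 7 also lists pathologists among the video readers, without saying whether they are the pathologists that Section 8 masks.

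**3. What the Section 4 match removes.** Consider a first pass with too little material, called diagnostic.
- If the nodule proves to be something else, the call does not match and the pass fails.
- If further passes or tests are needed to establish the diagnosis, the pass fails.
- If the call was malignant, sampling stopped and the nodule is later proven malignant, the call matches and the pass succeeds.

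The third case survives because the match tests whether the call was right, not whether the first pass alone was enough to make it. Section 4 assumes a malignancy prevalence of 0.5, so the case is not rare in principle.

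**4. Illustration.** The documents give no misreading rate, so the rates are assumptions. Let the true first-pass yield be 70% in both arms, with 59 per arm. Let f be the fraction of non-diagnostic first passes in the nCLE arm that are up-called and also survive step 3. The apparent nCLE yield is 0.70 + 0.30f, and the expected number of patients affected is 59 × 0.30 × f. The chance of a significant result favouring nCLE comes from exact enumeration of two binomials, with the test at two-sided 0.05.

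| f (assumed) | Patients affected | Apparent nCLE yield | Uncorrected chi-square | Fisher |
|---|---|---|---|---|
| 0 | 0 | 70.0% | 2.6% | 1.6% |
| 5% | 0.9 | 71.5% | 3.9% | 2.5% |
| 10% | 1.8 | 73.0% | 5.7% | 3.7% |
| 20% | 3.5 | 76.0% | 11.3% | 7.6% |

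Section 4 names chi-square as the main test and keeps Fisher for counts below 5, so the chi-square column is the relevant one. At f = 20%, between three and four patients raise the chance about fourfold (11.3/2.6 = 4.3).

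**The case against.** The strongest reply is that the endpoint is not a bare on-site call. Section 8 asks for a definitive diagnosis, Section 5 places that after re-evaluation by pathology staff, and Section 4 adds histological confirmation and agreement with the final diagnosis. A sufficient-material call at ROSE is a stopping rule, not the endpoint. This stands in part. An over-call does not pass unchecked into the primary result, and a reader who infers that it does goes further than the documents. But the objective still names ROSE, so the scoring reading is unsettled; neither reading is masked to arm; and the match lets through the case in step 3.

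A reader might also take larger up-call rates and conclude that the false-positive risk is very high. With f at 30% or 40% the same calculation gives 20.5% or 34.0%. Those figures require all such up-calls to survive the Section 4 conditions, all in one arm and one direction, and nothing in the documents supports rates of that size.

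Two further limits are fair. The plan does mask other readers (the video raters), so it cannot be said to contain a single masking statement. And Section 5 says that the research protocol will not interfere with routine pathology, so a remedy must not alter the clinical read.

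**Conclusion.** The point holds as a gap in masking, not as evidence of bias. Whichever reading scores the first pass, nothing keeps its reader from knowing the arm, and the match to the final diagnosis is a partial safeguard. On assumed surviving up-call rates of 5% to 20%, with no true effect, the chance of a significant result favouring nCLE is 3.9% to 11.3%, against 2.6% with none. That rests on a 70% true yield in both arms, 59 per arm, up-calling in the nCLE arm only and the uncorrected chi-square test. That the ROSE reader can recognise the arm is inferred from the visible differences and the absence of a described sham; the documents neither call the trial open-label nor say where the reader sits. Figure 3 and some introductory text were not available. The change is worth making because it is cheap and because a positive primary result would otherwise be open to the charge of reader expectation.

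**What to change.** - **Section 8, masking.** Extend the sentence to say that the study pathologists scoring the first pass will be unaware of both arm and nCLE results. State whether they are separate from the pathologists who review nCLE videos.
- **Section 8, Section 4 and both statements of the primary objective.** State that the primary first-pass result is scored from the separately labelled first-pass material at the existing pathology re-evaluation, with coded labels carrying no arm or nCLE information. It should not be scored from whether the unmasked operator took another pass. Changing Section 8 alone would leave ROSE in the objectives and create a contradiction.
- **Order of reading.** Where this can be done without changing the routine clinical read, record the first-pass call before the later passes are reviewed.
- **ROSE.** Keep it for directing the procedure, and report ROSE-based first-pass yield as a sensitivity analysis.

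**Cost.** Slide coding and a data-entry step, and a primary result that is available later than in the room. The re-evaluation is already planned, and Section 4 already provides that "Every needle pass at a location will be reported separately and entered into a database to provide yields after each sequential pass", so no extra samples or patients are needed. No extra reader is needed either, provided that the coded scoring fits within that re-evaluation.

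**Limitation to state in the plan.** Unmasked ROSE still influences when sampling stops, so cumulative yields and pass counts remain open to this bias.

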Suppose a patient suspected of lung cancer has a negative result of the bronchoscopic procedure. In that case, a surgical procedure (mediastinoscopy or lobectomy/pneumectomy with lymph node dissection) could follow to obtain tissue. This surgical procedure will be performed regardless of the result of nCLE imaging. If a surgical procedure is indicated, we will collect the histological images to compare with nCLE imaging. This study will not interfere with the standard cytology or the standard histology process. Digital copies of the cytological and histological slides of the measured nodules will be obtained and compared with the frames of the nCLE sequences.

Final Diagnosis or Definitive Diagnosis

For this 12-month analysis, pathology results of Robotic-aided biopsy samples that will be diagnostic of a non-malignant condition or indeterminate will be referred to as negative for malignancy or negative for brevity. Follow-up will be conducted to determine the final diagnosis (malignant or non-malignant). All cases will be followed according to the practitioner's judgment and standard of care testing (e.g., surgical tissue biopsy, repeat Robotic, CT-guided transthoracic needle biopsy or aspiration (TTNA), serial CT imaging, and lung health visits). Cases with subsequent diagnostic tests confirming a non-malignant diagnosis or without lesion progression on radiographic follow-up will be considered true-negative at 12 months, consistent with prior Robotic studies. If the follow-up diagnostics reveal malignancy or lesion growth on repeat imaging with appropriate follow-up diagnostic testing, this will be considered a false-negative. The following will also be regarded as false-negative: death due to lung cancer within 12 months; treatment without a confirmed diagnosis; and new diagnosis of cancer in the lung from any site (including non-index lesions or lymph nodes diagnosed as malignant by linear bronchoscopy during or after the index procedure).

Twelve-month diagnostic yield will be calculated per subject as the rate of true-positives (for malignancy) plus true negatives (for malignancy) of all subjects with attempted lung lesion biopsies.

Adverse Events

Definitions

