The tumor board will determine intermediate diagnosis and management recommendations for each patient at the intermediate and final diagnosis phases (see Figure 3). Three therapeutic management options will be considered: "neither treatment nor follow-up", "follow-up", or "treatment" (see above). If the diagnosis is certain, "neither surgery nor surveillance" will be recommended for benign nodules; treatment will be recommended for malignant lesions; either treatment or follow-up will be recommended for indeterminate nodules.

An intermediate diagnosis and an intermediate management recommendation will be provided after the tumor board receives TBNA histological results and recorded in the Case Report Form for each patient of both arms.

A final diagnosis and a final management recommendation will be provided just after the final diagnosis results are received by the tumor board and recorded in the Case Report Form for each patient of both arms.

These intermediate diagnosis and management recommendations will also be compared to the definitive diagnosis and final patient management decisions.

7. Statistical Analysis

Population demographics comparison in both arms:

Statistical analysis will be performed to compare the patient population in terms of demographics to assess whether there are any differences between the populations of the two arms in terms of age, sex, race, type of lung cancers, and cancer prevalence.

Lesion characteristics comparison in both arms:

Statistical analysis will be performed to compare the lesion characteristics to assess whether there is any difference in lesion characteristics between the two arms, in terms of size, location of the nodule, Presence of bronchus sign on computerized tomography, lung zone, positive PET, associated lymphadenopathy, distance closest to fissure, distance from lesion to pleura, and pre-procedure probability of malignancy.

Navigation Accuracy

Distance between the tip of the locatable guide/nCLE Confocal MiniprobeTM and the targeted lung lesion will be measured for each nodule. The median and standard deviation of the distance will be calculated for both arms. Using a statistical test (Student T-test), they will be compared between arms (Robotic-guided TBNA and Robotic-nCLE-guided TBNA).

Navigation success

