Per patient diagnostic yield of each bronchoscopic procedure (Robotic-guided TBNA and Robotic-nCLE-guided TBNA) will be calculated, and the accuracy of each technique using the final/definitive diagnosis as the reference. The diagnostic yield and accuracy for each method will be compared.

Patient management:

Three therapeutic management options will be considered right after the Robotic-guided TBNA or Robotic-nCLE-guided TBNA: 'neither treatment nor follow-up', 'follow-up', or 'treatment' (see section 6). If the diagnosis is certain, 'neither surgery nor surveillance' will be recommended for benign nodules; treatment will be recommended for malignant lesions; either treatment or follow-up will be recommended for indeterminate nodules.

Overall diagnostic and therapeutic management proportion differences in the two patient populations (Robotic-guided TBNA arm and Robotic-nCLE-guided TBNA arm) will be compared using a chi-square test. Differences between Robotic-guided TBNA and Robotic-nCLE-guided TBNA arms regarding the specific diagnostic and therapeutic management categories will be compared using McNemar's test.

Safety:

One of the secondary goals of the study is to evaluate the safety of Robotic-nCLE-guided TBNA in comparison to Robotic-guided TBNA. According to the validated Common Terminology Criteria for Adverse Events scale (CTCAE: https://ctep.cancer.gov/protocolDevelopment/electronic_applications/docs/CTCAE_v5.0.xlsx). The primary serious adverse event of concern is treatment-induced pneumothorax. Based on data from a recent sizeable multicentric study [27], Robotic-related Common Terminology Criteria for Adverse Events grade 2 or higher pneumothoraces (requiring admission or chest tube placement) occurred in 2.9%. The Robotic-related Common Terminology Criteria for Adverse Events grade 2 or higher bronchopulmonary hemorrhage and grade 4 or higher respiratory failure rates were 1.5% and 0.7%, respectively. Based on these results, we assume that the pneumothoraces rate among similar patients undergoing Robotic-nCLE-guided TBNA procedures will be equivalent to that study.

9. Study Benefit/Risk Ratio

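### The third endpoint counts changes in diagnosis and plan due to nCLE, but no patient has a tumour-board diagnosis and plan recorded both without and with nCLE

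*Combined protocol and SAP*

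**What the plan says.** The third endpoint (section 8, End Points) concerns patient management. Its purpose is to gauge how nCLE affects care, through "determining the proportion of patients with a correct change in definitive diagnosis and the associated change in management plan with nCLE". The same section states that "The definitive diagnosis will serve as the reference standard for the calculation of study endpoints".

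The records behind it are described in section 6, Diagnostic and Therapeutic Management. The first is early: "An intermediate diagnosis and an intermediate management recommendation will be provided after the tumor board receives TBNA histological results", and it is "recorded in the Case Report Form for each patient of both arms". The second is late: "A final diagnosis and a final management recommendation will be provided just after the final diagnosis results are received by the tumor board", again for both arms. One within-patient comparison is planned: "These intermediate diagnosis and management recommendations will also be compared to the definitive diagnosis and final patient management decisions".

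Section 8, Patient management, words the timing differently: "Three therapeutic management options will be considered right after the Robotic-guided TBNA or Robotic-nCLE-guided TBNA", with a pointer back to section 6.

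Section 7, Patient diagnostic and management analysis, compares proportions between arms by chi-square and specific categories between arms by McNemar's test. It gives no rule for scoring a correct change.

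Section 5 has the on-site image interpretation recorded, and has the bronchoscopist judge whether malignancy is present. On surgery after a negative bronchoscopy, section 5 (Histological evaluation) says: "This surgical procedure will be performed regardless of the result of nCLE imaging".

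**The concern.** The endpoint is worded as a count of patients who changed, with the change credited to nCLE. That calls for two states in the same patient, one without nCLE and one with it. The text schedules no such pair of board diagnoses and plans.

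The analyst would then have to decide what the endpoint means, possibly after seeing data. Two substitutes are at hand. One is a between-arm comparison, which rises if nCLE helps. The other is change from intermediate to final within a patient, which is the only within-patient comparison the plan describes and which falls if nCLE helps. A clinical-impact endpoint should not be open to two scorings that point in opposite directions.

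**Working it through.** **Step 1. The plan's own figure.** No number is stated for the third endpoint. The only design figure is 59 per arm for first-pass yield of 70% v 90%, 80% power, two-sided 0.05 (section 4, Sample size calculation). The unpooled two-proportion formula gives (0.7×0.3 + 0.9×0.1) × (1.960 + 0.842)² / 0.20² = 0.30 × 7.849 / 0.04 = 58.87 (unrounded normal quantiles), so 59. The figure is reproduced and does not bear on this point.

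**Step 2. What is recorded, and when, relative to nCLE.**

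| Record | nCLE arm | Control arm |
|---|---|---|
| Probability of malignancy before the procedure (section 6) | before imaging, but neither a diagnosis nor a plan | same |
| On-site nCLE read (section 5) | a judgement on malignancy; no plan tied to it | none |
| Intermediate board diagnosis and plan (section 6) | after imaging | no nCLE |
| Final board diagnosis and plan (section 6) | after imaging | no nCLE |

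No patient has a board diagnosis and plan on both sides of nCLE. The control arm supplies diagnoses and plans without nCLE, but in other patients. It can show a difference in proportions, not that an individual changed.

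**Step 3. The reference.** The definitive diagnosis is what study endpoints are scored against. A correct change *in* that diagnosis would have to be judged against itself. Only an earlier diagnosis can be corrected towards it.

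**Step 4. If intermediate-to-final change is scored.** Let *a* be the share of patients whose intermediate diagnosis is already right, and *c* the share of the rest who later move to the right diagnosis. Then

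share with a correct change = (1 − a) × c.

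For fixed *c* this falls as *a* rises, and it is zero when *a* = 1.

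Assumptions for illustration: the first-pass yields stand in for *a*, and *c* = 1.

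- Control: 1 − 0.70 = 30%; 59 × 0.30 = 17.7, about 18 of 59.
- nCLE: 1 − 0.90 = 10%; 59 × 0.10 = 5.9, about 6 of 59.

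Other assumed values of *a*, still with *c* = 1:

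| a, control / nCLE | Change, control | Change, nCLE |
|---|---|---|
| 80% / 90% | 20% (11.8 of 59) | 10% (5.9 of 59) |
| 85% / 95% | 15% (8.85 of 59) | 5% (2.95 of 59) |
| 70% / 70% | 30% (17.7 of 59) | 30% (17.7 of 59) |

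Section 5 (Final Diagnosis) classes indeterminate results as negative. If so, an undiagnosed patient whose nodule proves benign does not change. With the plan's assumed malignancy prevalence of 0.5 applied to the undiagnosed, *c* = 0.5: 17.7 × 0.5 = 8.85 and 5.9 × 0.5 = 2.95, about 9 v 3.

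The size depends on the assumptions. Whenever the nCLE arm is better at the intermediate stage and *c* is the same in both arms, the direction does not.

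**The case against.** Much can be said for the plan.

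- **Decisions without nCLE do exist.** A reader might infer that the trial holds no diagnosis or plan made without nCLE, so that nothing about clinical impact can be computed for any of the 118 patients. The documents do not support that. Control-arm records are made without nCLE. In the nCLE arm the on-site read is recorded beside pathology that is blind to it (section 8), so a diagnostic reclassification could be derived and checked against the definitive diagnosis. This stands. What is still missing is a management plan tied to that read.
- **The reversal rests on a scoring rule that the plan does not state.** It compares intermediate with final, but nowhere names that comparison as the third endpoint. The wording could also be meant as nCLE arm against control. This stands: the reversal is conditional.
- **18 v 6 is generous.** The yields are first-pass, whereas the intermediate record follows the whole procedure, over which yield is expected to rise to a plateau. Not every undiagnosed patient need change. This stands.
- **Clinical impact is partly covered elsewhere.** Secondary objectives 2 and 3 and section 7 compare treatment, follow-up and management between arms. True, but those are not the endpoint that section 8 names.
- **The timing conflict is mild.** Considering options straight after the procedure and recording a board recommendation after histology could be separate steps, and section 8 points back to section 6.
- **Surgery going ahead regardless of the nCLE result is weak evidence.** It covers only negative bronchoscopies, and nCLE could alter plans through better samples without the board seeing the read.
- **Figure 3 was not available here.** The text around it names only the intermediate and final phases, but the figure should be checked for any further record.

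**Conclusion.** The point holds in a limited form. As worded, the third endpoint cannot be obtained from the scheduled board records, because no patient has a diagnosis and plan both without and with nCLE, and because the item said to change correctly is itself the reference.

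That the endpoint runs backwards is not a property of the plan as written. It follows only if intermediate-to-final change is scored. In that case, 30% v 10% is an illustration built on first-pass yields and complete later correction; whole-procedure figures would probably be lower and closer together.

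A reader might also infer that the trial's main result is compromised. It is not: the primary endpoint, sample size and safety assessment are untouched. This should be fixed before the data are analysed, but it is not critical.

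**What to change.** Restate the third endpoint as the proportion of patients in each arm whose intermediate diagnosis and intermediate recommendation agree with the final diagnosis and final recommendation. Remove the reference to a change attributed to nCLE. Compare the arms as independent groups, by chi-square or Fisher's exact test, with a confidence interval for the difference; McNemar's test has no pairs here. Under the illustrative values and *c* = 1 the diagnosis part would read 70% v 90%, so it moves in the right direction.

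Say how an indeterminate intermediate diagnosis is counted, since that choice alone halves the illustrative counts in step 4.

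State one time for the intermediate record, the same in both arms and before later test results are known, and reconcile the wording of section 6 and section 8 (Patient management) accordingly.

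The cost is endpoint wording and one case report form timing instruction, with no new visit, procedure or patient. The small loss is that the endpoint becomes a between-arm agreement rate and makes no claim about changes in individual patients.
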